2.3.3 Primary Safety Endpoint

The primary safety endpoint is defined as the incidence of MAEs (listed in Section 10.1 and defined in Section 1.5.3 of the study protocol) for subjects undergoing the convergent procedure (EPi-Sense-AF) for the procedural to 30-day post-procedure time period. All MAEs will be adjudicated by the Clinical Events Committee (CEC), thus maintaining the objectivity of the primary safety endpoint.

2.3.4 Secondary Safety Endpoint

The secondary safety endpoint for the study will be the incidence of serious adverse events (SAEs) in the study through the 12 month post-procedure visit, in each treatment arm of the study.

2.3.5 Exploratory Endpoints

The exploratory endpoints are:

- Success or failure to achieve a 90% reduction from baseline AF burden with and without Class I/III AADs at 18 months post-procedure.

- Change in left ventricular ejection fraction (LVEF).
- Atrial remodeling assessed by a decrease in left atrial size.
- Health Economics Data
 - Change in number of hospitalizations and total number of days hospitalized for the 12 months post-procedure period (6 months to 18 months post-procedure) compared to the number of hospitalizations in the 12 months prior to the procedure.
 - Change in rhythm disturbance treatments (e.g. electrical or pharmacological cardioversion, AAD therapy, supraventricular ablative therapy) 12 months post-procedure period (6 to 18 months post-procedure) compared to 12 months prior to the procedure.

Additional exploratory endpoints, pending availability and usability of appropriate data, will include:

- Freedom from AF/AFL/AT requiring intervention (emergency visits, cardioversion, urgent care visit, re-ablation, etc.).
- Significant reduction in AF burden: 75% reduction from pre- to post-ablation, evaluated at 6 and 12 months.
- Total post-ablation burden of 12%, evaluated at 6 and 12 months.
- Freedom from stroke-relevant AF/ AFL/AT-duration (cutoff of 1 hour).
- Regression of AF: conversion of persistent to paroxysmal AF.
- Prevention in AF progression: time to first episode of persistent AF.

3 STUDY DESIGN

3.1 Overall Study Design

This study is a prospective, open-label, 2:1 randomized (convergent procedure [EPi-Sense-AF] versus stand-alone endocardial catheter ablation [catheter ablation]), multi-center pivotal clinical study. The study will enroll and randomize one hundred and fifty three (153) subjects from up to thirty (30) sites, approximately twenty-seven (27) in the United States and three (3) international sites.

Subjects in both arms of the study will be evaluated post-procedure at 7 days; 1, 3, 6, and 12 months; a long-term follow-up visit at 18 months; and long-term phone follow-ups at 2, 3, 4, and 5 years.

The study design includes a pre-procedure period (screening/baseline assessments within 90 days of the planned procedure, randomization, and pre-procedure [intra-op exclusion] visit); the procedure visit (day 0); a post-procedure follow-up period (including a 3-month blanking period); and a long-term follow-up period. The study design is illustrated in Table 1. Refer to Table 1 and Table 2 for further details.

Table 1 Study Data Collection Requirements

	Baseline	Pre-procedure	Procedure	7 Days	1 month	3 months	6 months	12 months
Informed Consent for Study Participation	X							
Inclusion/Exclusion Criteria	X	X	X					
Medical History	X							
Spiral CT or MRI	X						X	
Procedure			X					
ECG	X		X		X	X	X	X
ECHO (TTE)	X			X			X	
ECHO (TEE)		X						
24 hr Holter monitor	X						X	X
Documentation of any AF treatments					X	X	X	X
Medications (selected)	X		X	X	X	X	X	X
Evaluation of AEs			X	X	X	X	X	X
Six minute walk test	X							X
QoL assessments	X							X

Note: TTE=trans-thoracic echocardiogram; TEE=trans-esophageal echocardiogram. QoL assessments include SF-36 and AFSS.

Table 2 Continued Long Term Data Collection Requirements

	18 months	Phone Follow-up 2 years	Phone Follow-up 3 years	Phone Follow-up 4 years	Phone Follow-up 5 years
Health Status	X	X	X	X	X
ECG	X				
Rhythm Status	X	X	X	X	X
7 day Holter monitor	X				
Medications (selected)	X	X	X	X	X
Evaluation of AEs	X	X	X	X	X

3.2 Schedule of Study Assessments

Pre-Procedure Period:

Subjects meeting enrollment criteria described in protocol sections 4.2-4.4, who have agreed to study participation and signed the informed consent, will be considered enrolled in the study. Baseline evaluations will then be completed to further determine study procedure eligibility, as described in protocol section 4.5. These baseline assessments (i.e., the Baseline Visit) must be completed within 90 days of the study procedure.

Randomization will be implemented using Tempo™, the electronic research tool used for collecting clinical data. Randomization will be blocked by investigator site on randomly chosen blocks of 3 or 6 patients allocated 2:1 to the treatment arms, respectively. Appropriate randomization codes will be provided on the screen immediately after randomization for a subject is requested. The treatment arm code will be automatically stored in the study database.

A trans-esophageal echocardiograph (TEE) or intra-cardiac echocardiograph (ICE) will be performed immediately pre-procedure for intra-op exclusion purposes (i.e., Pre-Procedure Visit). If the subject meets either of the intra-op exclusion criteria specified in protocol section 5.1, the subject will not undergo a study procedure.

Patients becoming ineligible for a study procedure as a result of meeting the study intra-op exclusion criteria will be replaced. They will be followed for 30 days post-TEE or post-ICE, and information collected will be included in the study listings.

Study Procedure (Day 0):

Once the procedure intra-op exclusion conditions have been evaluated, and the subject is determined to be eligible to proceed with the study, the study procedure will be scheduled and performed. See the protocol sections 5.2 and 5.3 for a more detailed description of each treatment arm procedure.

Post-Procedure Follow-up Assessments:

Subjects are evaluated at 7 days (7 days + 7 days post-procedure), 1 month (30 days + 7 days post-procedure), 3 months (90 days \pm 15 days post-procedure), 6 months (180 days \pm 30 days post-procedure), and 12 months (365 days \pm 30 days post-procedure). A long-term follow-up visit is also conducted at 18 months (day 550 \pm 30 days post-procedure) and long-term phone follow-up at 2, 3, 4, and 5 years (\pm 30 days) post-procedure. In all cases, post-procedure refers to the index (study) procedure.

The period from index procedure through the 3-month post-procedure visit will be considered a blanking period, as described in Section 7.4.2. During this time, the use of AADs, cardioversions, and any recurrence or episodes of AF will not be considered a treatment failure. Subjects who receive AF therapy following the 3 month blanking period through the 12 months post-procedure follow-up visit will be considered primary efficacy failures, as described in Sections 7.2 and 9.1.

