### 1.3 Study Design

This is a, prospective, open label 2:1 randomized (convergent procedure versus standalone endocardial catheter ablation) multi-center pivotal clinical study. The study will enroll and randomize one hundred and fifty three (153) patients from up to thirty (30) sites, twenty-seven (27) US and three (3) OUS.

Potential subjects with symptomatic persistent AF will be screened by the sites for study participation. Consented subjects meeting all inclusion / exclusion criteria will be enrolled and randomized into the study.

Subjects in both arms of the study will be evaluated post procedure at 1 month, 3 months, 6 months and 12 months with a long-term follow-up visit at 18 months and long-term phone follow-up at 2, 3, 4, 5 years as detailed in this protocol. Submission for premarket approval will be filed after study subjects in both arms of the study complete the one year post procedure follow-up visit.

Annual reports will be submitted to the Agency in compliance with FDA regulatory requirements. One month safety data for the first 50 subjects in the treatment arm will be submitted to the FDA for review. During the conduct of this randomized study, any reported death, pericardial effusion leading to therapeutic drainage, atrio-aesophageal fistula or stroke will be reported to the Agency within 10 days.

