#### **4.6 Subject Randomization**

Subjects who have consented to study participation, have met all inclusion/exclusion criteria and have completed all baseline evaluation and are eligible for study participation will be randomized to either the convergent procedure or standalone endocardial catheter ablation procedure.

Randomization will be implemented using Tempo™, the electronic research tool used for collecting clinical data. Randomization will be blocked by investigator site on randomly chosen blocks of 3 or 6 patients allocated 2:1 to the treatment arms, respectively. Appropriate randomization codes will be provided on the screen immediately after randomization for a subject is requested. The treatment arm code will be automatically stored in the study database.

Subjects becoming ineligible for the convergent or the endocardial catheter ablation procedure as a result of meeting the study intra-op exclusion criteria will be replaced.

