### **12.7 Screened Subjects Who are Not Enrolled**

Only data for enrolled/randomized subjects will be monitored and entered into the database. Subjects who are screened for the study but are not enrolled for any reason will not be followed and AtriCure will not evaluate their data. The sites may retain the screening data forms for these subjects, at their discretion.

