5.4 Safety Population

The Safety population will include all subjects who receive a randomized study

procedure (either EPi-Sense-AF or catheter ablation). Subjects will be analyzed according to procedure received, in the event it differs from the randomized procedure. This population will be used for all safety analyses.

6 **CONSIDERATIONS FOR DATA ANALYSIS**

6.1 **Programming Environment**

All analyses will be conducted using SAS® version 9.3 or higher.

6.2 **Strata and Covariates**

There are no planned stratified analyses or adjustments for covariates, other than the subgroup analyses specified in Section 6.3 and potential adjustments for geographical location discussed in Section 9.3.3. Additional subgroup analysis and covariate adjustments will be performed as necessary.

6.3 **Subgroups**

A subgroup analysis of the primary endpoint will be conducted for the subgroup variables of:

- Geographic location - Europe, Region of United States (such as West, Southeast, Northeast, Central/Midwest) as per SAP section 9.3.3.
- Gender (M vs F).
- Age at baseline visit (<65 vs \geq 65 years).
- Body mass index (BMI; <30 vs \geq 30 kg/m²) at baseline visit,
- Access type (transdiaphragmatic or sub-xiphoid, which will be collected from source documentation, entered in a spreadsheet, finalized prior to database lock, and incorporated into analysis datasets).
- Left atrium size (< median value vs \geq median value, as recorded on the Pre-Procedure echocardiogram, based on the median of the ITT population). Other clinically relevant cut-points may be defined prior to unblinding the study.
- Left atrial volume (<median value vs \geq median value, as recorded on the CT Scan or MRI at the Baseline visit, based on the median of the ITT population). Other clinically relevant cut-points may be defined prior to unblinding the study.
- AF classification (Persistent versus Long-standing persistent AF).

For each of these, a logistic regression model will be fit to the primary endpoint, modeling for (1) treatment arm, (2) subgroup variable (dichotomous), and (3) interaction term of treatment arm * subgroup variable. A two-tailed alpha level of 0.15 will be used for determining poolablity of results. If the p-value of the interaction

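### Block sizes of 3 or 6 within site are disclosed to sites in an open-label trial, leaving an avoidable but limited route to selection bias in the primary comparison

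*SAP*

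**What the plan says.** SAP 3.2 gives the scheme in full: "Randomization will be blocked by investigator site on randomly chosen blocks of 3 or 6 patients allocated 2:1 to the treatment arms, respectively". Protocol 4.6, which every site works from, has the same sentence. Neither document says that the sizes are withheld from sites.

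Protocol 1.3 describes a "prospective, open label 2:1 randomized (convergent procedure versus standalone endocardial catheter ablation) multi-center pivotal clinical study", and SAP 3.1 agrees. On how the arm is revealed, SAP 3.2 says: "Appropriate randomization codes will be provided on the screen immediately after randomization for a subject is requested". Before that point, Protocol 4.6 requires that subjects have consented, and only those who "have met all inclusion/exclusion criteria and have completed all baseline evaluation and are eligible for study participation will be randomized".

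The 153 subjects are to be "patients from up to thirty (30) sites". On subjects screened but not enrolled, Protocol 12.7 says that they "will not be followed and AtriCure will not evaluate their data". The primary test in SAP 9.1 is an unadjusted chi-square test, or Fisher's exact test if cells are sparse. SAP 6.2 states: "There are no planned stratified analyses or adjustments for covariates", apart from the subgroup analyses and a possible geographic adjustment.

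**The concern.** Permuted blocks protect against selection only while the person entering patients cannot work out what comes next. Here a site knows three things: its list is its own, its blocks are 2:1 and of size 3 or 6, and which arms it has already received. It also controls timing. Protocol 4.5 asks only that baseline fall within 90 days of the procedure, and neither document sets a deadline between confirmed eligibility and the randomisation request. An eligible patient can therefore be held back or brought forward according to the arm expected.

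If that were done by prognosis, the arms would differ at entry and an unadjusted test would count the difference as a treatment effect. Independent Holter review (Protocol 1.5.1) protects the reading of outcomes, not who enters each arm. Because the sponsor does not evaluate screened, non-enrolled patients, selective presentation would leave little trace. The trial is a pivotal superiority study intended to support a premarket application.

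**Working it through.** **The plan's own figures.** SAP 4 assumes 40% against 65% success, two-sided alpha 0.05, 80% power, 2:1 allocation and 10% dropout. The pooled-variance normal formula without continuity correction gives 45.7 controls before rounding; 45.7/0.9 = 50.8, so 51, and 102:51 = 153. The plan's number reproduces, and this point does not alter it. The design difference of 65 - 40 = 25 points is the yardstick below. With all 30 sites used, the average is 153/30 = 5.1 patients per site.

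**Assumption.** The documents do not give the chance of drawing each block size. I take P(block of 3) = 1/2, with a range of 1/3 to 2/3.

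**Predicting the next arm in a site's first block.** Write T for convergent and C for control.

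- P(TT) is 1/3 in a block of 3 and (4/6)(3/5) = 0.4 in a block of 6. The next is C with probability 1 and 2/4 respectively. So P(C | TT) = (0.5 x 1/3 x 1 + 0.5 x 0.4 x 0.5) / (0.5 x 1/3 + 0.5 x 0.4) = 0.2667/0.3667 = 73%, against 33% unconditionally.
- A first C has probability 1/3 under either size. So P(T | C) = 0.5 x 1 + 0.5 x 4/5 = 90%, against 67%.
- CC can occur only in a block of 6, so T is then certain. That start has probability 0.5 x (2/6)(1/5) = 3.3%.

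**All histories, by exact enumeration (50:50 mix).**

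| Patient at site | 1 | 2 | 3 | 4 | 5 | 6 |
|---|---|---|---|---|---|---|
| Allocation certain | 0 | 0 | 3.3% | 10% | 13.3% | 21.7% |
| Best guess correct | 67% | 67% | 83% | 70% | 70% | 92% |

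Over a site's first 5 patients:

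- Certain: (0 + 0 + 3.3 + 10 + 13.3)/5 = 5.3% (3.6-7.1% over the range of block mixes). Certain control is 0.7%.
- Best guess correct: (66.7 + 66.7 + 83.3 + 70 + 70)/5 = 71%. Always guessing convergent gives 67%.
- Probability of convergent at least 15 points from 2/3: 40% (38-42%). About 29 of those 40 points are cases where convergent, already the likelier arm, becomes likelier still. Control is the likelier arm in 10% of allocations.

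Over a site's first 12 patients, 8.9% are certain and the best guess is right 75% of the time. Fewer, larger sites would therefore raise exposure.

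**What steering could do.** I simulated the primary comparison with no true effect, 50% success and 30 sites of 5. A steering site enters a patient with a better chance of success when convergent is more likely than 2/3, and one with a worse chance when it is less likely. False superiority means a significant result favouring convergent (nominal 2.5%). The prognosis shifts and the share of sites steering are assumptions.

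| Who steers, and when | Shift | Bias | False superiority |
|---|---|---|---|
| All sites, probability more than 5 points from 2/3 | 5 points | about 3 points | about 5% |
| Same | 10 points | about 6.5 points | about 11% |
| Same | 15 points | about 10 points | about 20% |
| All sites, at least 15 points from 2/3 | 10 points | about 5 points | about 9% |
| All sites, more than 30 points from 2/3 | 10 points | about 2.5 points | about 5% |
| One third of sites, 5-point rule | 10 points | about 2 points | about 5% |
| One fifth of sites, 5-point rule | 10 points | about 1 point | about 4% |

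The 5-point rule acts on 64% of allocations. It is looser than the 15-point cut behind the 40% figure, so its rows are upper limits for the shift stated.

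**The case against.** The strongest reply is that the scheme already has protections and that they work fairly well. Allocation is electronic and one subject at a time. Block size varies at random. A subject must have consented, met eligibility and completed baseline first. Fixed blocks of 3 would make 44% of allocations certain, and fixed blocks of 6 would make 29% certain (over complete blocks). The mixture brings this to about 5% at 5 patients per site. A site often cannot tell where a later block begins: after TTC, TCT or CTT the prediction is exactly 2/3 again. Measured imbalance would show in the baseline summaries by arm (SAP 8.4). SAP 6.2 allows further covariate adjustment as necessary, SAP 6.3 fits logistic models with age, BMI, left atrial size and volume, and AF classification, and SAP 9.3.3 allows a site or region covariate.

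Much of this stands, and it limits the size of the problem. It does not close the route. The checks before randomisation do not govern which eligible patient is presented next, or when. The third patient at a site is still guessed correctly 83% of the time and the sixth 92%. The further adjustments are optional or built for subgroups, and none is committed to as a check on the primary result.

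A reader might go further and infer that sites can predict many allocations, or that the primary comparison is biased. The documents support neither. Certainty is uncommon, overall guessing gains only about 4 points at 5 patients per site, and nothing shows or suggests that any site steered. Nor should the sizes be called public on this ground: the protocol is marked confidential, and the point is disclosure to the people who enter patients.

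**Conclusion.** The concern holds as a limited, avoidable weakness in allocation concealment. That the sizes are disclosed to sites, by site, in an open-label trial is plain from the text. The predictability figures rest on one assumption, the block mix, and barely move across its range; predictability is concentrated at a site's third and sixth patients.

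The bias figures are conditional. They need sites to steer by prognosis and all in the same direction, and they depend on an assumed shift and a 50% success rate. The plausible partial case of 1-2 points is small against the 25-point design difference, but it still lifts false superiority from 2.5% to about 4-5%. That justifies a change when the change is cheap; it does not justify doubting the result by itself.

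**What to change.** Remove the block sizes from Protocol 4.6 and SAP 3.2. State only that permuted blocks of varying size are used within site, and hold the sizes in a restricted randomisation file. This is a wording change and leaves the sample size at 153.

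Deleting the text does not undo what sites have read, and the documents do not give recruitment status, so the next step depends on it:

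- **If randomisation is still open:** generate the blocks not yet used from an undisclosed set that includes a further multiple of 3. The cost is a new list in the data capture system and a slightly larger possible within-site departure from 2:1.
- **If randomisation is complete:** add to SAP 9.3 a sensitivity analysis of the primary endpoint, adjusted for site or pooled site and for baseline prognostic variables already collected, such as left atrial size, AF classification and age. This needs no new data. It addresses measured imbalance only, so it supports the primary test without removing the risk from unmeasured prognosis.

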4 SAMPLE SIZE CONSIDERATIONS

A sample size of 153 subjects is planned for this study, which is based on the primary endpoint of AF/AFL/AT freedom.

It is assumed that the success rate for the control arm (catheter ablation) is 40%,

and the study is designed to document superiority of EPi-Sense-AF with a 65% success rate. The sample size result, based on 2-sided $\alpha = .05$, 80% power, a 2:1 allocation of EPi-Sense-AF:catheter ablation, and a 10% drop out rate, is 102:51 or 153 subjects.

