## 9.2 Sample Size Justification

The sample size is determined taking into consideration the primary endpoint of complete elimination of AF burden. It is assumed that the success rate for the Control arm is 40%, and the study is designed to document superiority of EPi-Sense-AF with a 65% success rate. The sample size result, based on 2-sided  $\alpha = .05$ , 80% power, a 2:1 allocation of EPi-Sense-AF:Control, and a 10% drop out rate, is 102:51 or 153 subjects.

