7.2 Imputation of AF/ AFL/AT Freedom

Subjects who were randomized and received study procedure but have no post-treatment assessments will be conservatively imputed as having failed to achieve freedom from AF/ AFL/AT (e.g., treatment failure). Similarly, subjects who were randomized and received study procedure but do not have treatment assessments following the 3-month blanking period (as described in Section 7.4.2), or a visit was performed but insufficient information was collected to determine whether or not AF/AFL/AT was experienced and/or whether Class I/III AADs were administered, will also be imputed as treatment failures. Subjects who do not have complete information for the efficacy evaluation period (for example, withdrew before 12 months) but have sufficient information to conclude that they would be classified as *not* AF/AFL/AT free (such as: new or increased dose of Class I/III AAD or documented findings of AF/AFL/AT) will be considered treatment failures. These subjects will *not* be considered to have been imputed, for the purpose of tipping point or multiple imputation analyses, as it is clear that they would have been treatment failures even if complete information had been collected.

The same approach will be utilized to impute AF freedom for secondary efficacy analyses.

A tipping-point analysis will also be performed, as described in Section 9.3.2, which will be performed on un-imputed data. Further details on criteria for treatment failure are provided in study protocol Section 1.5.

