9.1 Primary Efficacy Analysis

The binary primary endpoint of success or failure to achieve freedom from AF/AT/AFL absent class I and III AADs except for a previously failed or intolerant class I or III AAD with no increase in dosage following the 3 month blanking period through the 12 months post procedure follow-up visit will be compared between the two treatment groups using a chi-square test using a two-sided alpha of 0.05 to determine if superiority of the treatment arm is attained. This is detailed in Sections 2.3.1 and 7.4.5 of the SAP.

The analysis will be performed on the ITT population. If necessary, imputation will be performed as specified in Section 7.2.

Define P as the true percentage of subjects failing to achieve AF/AFL/AT freedom, where P_T is the true failure rate for the treatment arm and P_C for the control arm. The hypothesis to test is:

$$H_0: P_T = P_C \quad \text{vs} \quad H_a: P_T \neq P_C$$

The formula for the chi-square test is:

$$\chi^2 = \sum_{i=1}^n \frac{(O_i - E_i)^2}{E_i}$$

where O_i represents the number of observed events in the i^{th} cell and E_i represents the expected number of events in the i^{th} cell. H_0 is rejected in favor of H_a if the resulting p-value < 0.05 and the estimated P_T exceeds P_C . If $E_i < 5$ for any cell (that is, if the [number of subjects in a treatment arm * total number of successes / total number of subjects] is < 5 , or similarly for the number of failures), then the Fisher's Exact test will be used in lieu of the chi-square test.

If the $p \leq 0.05$, we will conclude that the percentages differ significantly between treatment arms.

The number and percent of subjects achieving AF/AFL/AT freedom will be summarized by treatment arm, and individual results listed by subject.

The primary efficacy analysis will be repeated on the specific subgroups as described in Section 6.3.

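### The 153-subject calculation removes dropouts, but the primary analysis counts treated dropouts as failures; if all 10% are lost after the procedure, power is about 74–75%, not 80%

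*SAP*

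**What the plan says.** **Sample size.** SAP 4 assumes 40% success with catheter ablation and aims to show "superiority of EPi-Sense-AF with a 65% success rate", with two-sided alpha 0.05 and "80% power, a 2:1 allocation of EPi-Sense-AF:catheter ablation". The result, "and a 10% drop out rate, is 102:51 or 153 subjects", is repeated in Protocol 9.2 ("a 10% drop out rate, is 102:51 or 153 subjects"). Neither section says when dropout is expected, how it enters the analysis, or whether 65% and 40% are rates in completers or rates after imputation.

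**Primary analysis.** Under SAP 9.1 the binary endpoint "will be compared between the two treatment groups using a chi-square test", in the ITT population, with missing outcomes imputed as in SAP 7.2.

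**Who is analysed.** SAP 5.1 (like Protocol 9.3.1) limits ITT to subjects who receive a randomized procedure.

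**What happens to missing outcomes.** Under SAP 7.2, treated subjects with no post-treatment assessments "will be conservatively imputed as having failed to achieve freedom from AF/ AFL/AT". The same section extends this to treated subjects with nothing after the blanking period and to visits that yield too little information. It does not itself name a subject who is recurrence-free at month 6 and then withdraws. That case is covered by SAP 7.4.5: success needs a clear result at both the 6 and 12 month visits, and a subject without them and without a failure is indeterminate and is sent to imputation under 7.2 and 9.3. Section 9.3 contains only sensitivity analyses, so for the primary analysis the 7.2 rule applies.

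**The concern.** Dividing by 0.9 is the right allowance when dropouts are removed: the sample shrinks and the two rates stay as assumed. It is not the right allowance when dropouts stay in the denominator as failures. The sample then keeps its size, but both success rates fall, and the difference between them falls in proportion.

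The plan therefore sizes the trial under one treatment of dropout and analyses it under another. This matters because the comparison is the primary endpoint of a single pivotal study meant to support a premarket approval application. A non-significant result would be read against a stated type II error of 20% when the true planning figure could be nearer 26%.

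**Working it through.** **Inputs.** p_T = 0.65, p_C = 0.40, 2:1, 80% power, 10% dropout, 102:51 (SAP 4); uncorrected chi-square, two-sided 0.05 (SAP 9.1). Expected cell counts are far above 5, so the switch to Fisher's exact test does not arise.

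**1. Reproduce 153.** The pooled-variance formula without continuity correction, for the control arm, is

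n_C = [1.960·√(p̄(1−p̄)·1.5) + 0.842·√(p_C(1−p_C) + p_T(1−p_T)/2)]² / (p_T − p_C)²

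with p̄ = (0.40 + 2×0.65)/3 = 0.567.

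- First term: 1.960 × √0.3683 = 1.190. Second term: 0.842 × √0.3538 = 0.501.
- n_C = 1.690² / 0.0625 = 45.7, rounded up to 46. With 92 on treatment, that is 138 evaluable.
- 138/0.9 = 153.3, which matches 102:51.

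Exact chi-square power at 92:46 is 80.2%. The stated 80% is therefore the power after dropouts have been removed.

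**2. Apply the SAP's rule to treated dropouts.** Assume that 65% and 40% are rates in completers, and that a share d of each arm is lost after the procedure, independently of outcome, and imputed as failure. The rates become 0.65(1−d) and 0.40(1−d), still at 102:51. At d = 10% they are 58.5% and 36.0%, and the difference falls from 25 to 22.5 points.

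Normal approximation at d = 10%, with p̄ = (0.36 + 2×0.585)/3 = 0.51:

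- Null SE = √(0.51×0.49×(1/51 + 1/102)) = 0.0857
- Alternative SE = √(0.36×0.64/51 + 0.585×0.415/102) = 0.0831
- Power = Φ((0.225 − 1.960×0.0857)/0.0831) = Φ(0.686) = 75.4%

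| Share of each arm imputed as failure | Rates (treatment vs control) | Exact power | Normal approximation |
|---|---|---|---|
| 0% | 65.0% vs 40.0% | 84.0% | 84.2% |
| 5% | 61.75% vs 38.0% | 79.3% | 79.9% |
| 10% | 58.5% vs 36.0% | 74.4% | 75.4% |
| 15% | 55.25% vs 34.0% | 69.7% | 70.5% |

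Power holds at 80% up to about 4% (exact, 80.2% at 4%) or about 5% (normal approximation).

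**3. Vary the timing of a 10% loss.** Subjects lost before the procedure are outside ITT.

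- All before: about 92:46 analysed at 65% vs 40%, power about 80%.
- Half before, half after: 0.95 × 102 = 96.9 and 0.95 × 51 = 48.5 treated, of whom 5/95 = 5.3% are imputed as failures. The rates are 61.6% vs 37.9%, and power is about 77–78%.
- All after: 102:51 at 58.5% vs 36.0%, power 74–75%.

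**4. Rates already net of imputation.** If 65% and 40% already count dropouts as failures and all dropout follows the procedure, nothing is lost: power at 102:51 is 84%, and the allowance for dropout was not needed.

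**The case against.** The strongest objection is about timing. Dropout is not defined, and both ITT and SAP 7.2 cover only subjects who received a procedure. Someone who withdraws between randomization and procedure leaves the primary analysis, and for that loss dividing by 0.9 is correct. This stands. A reader might infer that power simply is 74%, or that the sample size text is inconsistent however it is read. The documents support neither: if all losses come before the procedure, the stated 80% is right. Against that, intra-op exclusions are replaced (Protocol 4.6, SAP 3.2), so they do not use up the 10%, and nothing says that the 10% is meant as pre-procedure loss.

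Second, dropout may be related to outcome. SAP 7.2 treats a documented failure before withdrawal as a true failure, so if dropouts are mainly failures the loss is smaller. If each success rate falls by only about 4–5% of its value, instead of 10%, power is about 80%. This also stands, and it is why 74–75% needs its assumptions attached.

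Third, the tipping-point and multiple-imputation analyses in SAP 9.3 address missing data. They test the robustness of the result; they do not restore power to the primary test.

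A reader might also infer that the trial must grow. With all 10% imputed as failures, 80% power would need about 174 subjects (116:58), but that is context only. The type I error, the test and the analysis are unaffected.

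**Conclusion.** The point holds for dropout after the procedure. The plan's 80% is the power with dropouts removed, whereas the primary analysis keeps treated dropouts as failures. Power at 102:51 is about 74–75% if the whole 10% is lost after the procedure, about 77–78% if the loss is split evenly, and about 80% if all of it precedes the procedure.

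These figures assume that 65% and 40% are rates in completers, that dropout is equal in the two arms, and that it is independent of outcome. The documents state none of these. Equality matters: by normal approximation, imputing 10% on treatment and 5% on control gives 67.1%, and the reverse gives 86.1%. The arithmetic is firm. Which figure applies depends on facts that the plan leaves out, and that omission is itself the defect.

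**What to change.** In SAP 4 and Protocol 9.2, add:

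1. when the 10% dropout is expected, before or after the procedure;
2. that subjects lost after the procedure without a documented failure count as failures in the primary analysis, with a reference to SAP 7.2 and 7.4.5 (Protocol 9.4 names only subjects with no post-treatment assessments, so the protocol text needs that reference);
3. whether 65% and 40% are before or after this imputation.

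Then restate power at 102:51 to match. If the rates are in completers, give about 74–75% for 10% imputed failures, with the 74–80% range by timing and the assumptions of equal, outcome-independent dropout. If the rates already include imputed failures and all dropout follows the procedure, give 84%.

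The sample size stays at 153, and no visit or analysis changes. The cost is a stated power that is less favourable on the completer reading. Removing the dropout allowance while keeping 80% power would mean 138 subjects. That is a design change, not a wording change, and is not proposed.
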